#### Section B-8.12 Cohort status/switch of women during follow-up

Table B-8.12.1 Cohort status/switch of women during follow-up, AT population, Complete cohort

	DNG	OAED				NAED	Allocation unknown	Total	
		GnRH-a	Danazol	All OAED	CHC	Other progestin	All NAED		
Number (%) of women	xx ( 100%)	xx ( 100%)	xx ( 100%)	xx ( 100%)					
Switched or stopped EMT*	xx ( xx.x%)	xx ( xx.x%)	xx ( xx.x%)	xx ( xx.x%)					
Thereof									
Switch to DNG	xx ( xx.x%)	xx ( xx.x%)	xx ( xx.x%)	xx ( xx.x%)					
of which									
Within 6 months	xx ( xx.x%)	xx ( xx.x%)	xx ( xx.x%)	xx ( xx.x%)					
Within 7 and 12 months	xx ( xx.x%)	xx ( xx.x%)	xx ( xx.x%)	xx ( xx.x%)					
After 12 months	xx ( xx.x%)	xx ( xx.x%)	xx ( xx.x%)	xx ( xx.x%)					
Switch to GnRH-a	xx ( xx.x%)	xx ( xx.x%)	xx ( xx.x%)	xx ( xx.x%)					
of which									
Within 6 months	xx ( xx.x%)	xx ( xx.x%)	xx ( xx.x%)	xx ( xx.x%)					
Within 7 and 12 months	xx ( xx.x%)	xx ( xx.x%)	xx ( xx.x%)	xx ( xx.x%)					
After 12 months	xx ( xx.x%)	xx ( xx.x%)	xx ( xx.x%)	xx ( xx.x%)					
Switch to Danazol of which	xx ( xx.x%)	xx ( xx.x%)	xx ( xx.x%)	xx ( xx.x%)					
Switch to CHC of which	xx ( xx.x%)	xx ( xx.x%)	xx ( xx.x%)	xx ( xx.x%)					
Switch to Other progestins of which	xx ( xx.x%)	xx ( xx.x%)	xx ( xx.x%)	xx ( xx.x%)					

...

Supporting document SOP BMT 01.09 – Doc 5002.02 – Effective date 21.03.2017

Switch to other EMT\*' xx (xx.x%) xx (xx.x%

of which

•••

Note: \*Only the first switch or stop of the EMT prescribed at study entry is considered.

Note: "Women switched to other NAED, unspecific treatment (Multi-use, allocation unknown) or stopped EMT use (Ex-use).

Date of analysis:

Table B-8.12.2 Cohort status/switch of women during follow-up, AT population, Starter

Table B-8.12.3 Cohort status/switch of women during follow-up, AT population, Switcher

Table B-8.12.4 Cohort status/switch of women during follow-up, AT population, Restarter

Table B-8.12.5 Cohort status/switch of women during follow-up, AT population, Diagnosis confirmed by surgery

Table B-8.12.6 Cohort status/switch of women during follow-up, AT population, Diagnosis based on clinical symptoms

Table B-8.12.7 Cohort status/switch of women during follow-up, AT population, Germany

Table B-8.12.8 Cohort status/switch of women during follow-up, AT population, Poland

Table B-8.12.9 Cohort status/switch of women during follow-up, AT population, Hungary

Table B-8.12.10 Cohort status/switch of women during follow-up, AT population, Switzerland

Table B-8.12.11 Cohort status/switch of women during follow-up, AT population, Russia

Table B-8.12.12 Cohort status/switch of women during follow-up, AT population, Ukraine

Supporting document SOP BMT 01.09 – Doc 5002.02 – Effective date 21.03.2017

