#### Secondary objectives are:

- To characterize the baseline risk of users of the individual formulations (lifetime history of co-morbidity, risk markers, co-medication, socio-demographic and lifestyle data).
- To analyze the drug utilization pattern of DNG and other endometriosis treatments in a study population that is representative for typical use of the individual preparations under routine medical conditions.
- To investigate the risks of short and long-term use of DNG and of established endometriosis treatments in adolescent women.

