#### 5.1 Analysis sets

There are no specific inclusion or exclusion criteria. However, women with a language barrier, a non-hormonal or not newly prescribed baseline medication or women who are pregnant at study enrollment will be excluded from the analysis. The final analyses will include both an "as treated" (AT) and an "intention-to-treat" (ITT) analysis. All women who are not excluded from the analysis will be assigned to the ITT and AT population at baseline. Only women with follow up information will be considered for longitudinal analysis (e.g. distribution of outcomes over time, incidence rates, regression). Women who never started their prescribed baseline medication will be considered in the ITT analysis, but excluded from the AT analysis. The safety conclusions of the study will be based on the AT analysis.

Supporting document SOP BMT 01.09 – Doc 5002.02 – Effective date 21.03.2017

This study follows three cohorts: users of Visanne (DNG), users of other medication approved for the treatment of endometriosis (OAED) and users of non-approved hormonal medications prescribed for endometriosis treatment or those approved only in some participating countries (NAED).

Distribution of women, population characteristics (baseline and follow up) as well as clinical outcomes will be presented for the following cohorts and sub-categories.

Cohort Sub-category for presentation	
DNG	Complete cohort
OAED	GnRH-a, Danazol, complete cohort
NAED	Combined hormonal contraceptives, other progestins, complete

The cohorts consist of new users (starter and restarter) or switcher of a hormonal endometriosis treatment. For the primary analysis, outcomes of interest or adverse events will be assigned to the treatment at the time the outcome or the event occurred. Women with multiple exposure or unspecific treatment will be specified as "Allocation unknown". Women who stopped their treatment will be assigned to an "Ex-use" cohort.

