#### 5.4.4 Definition of secondary outcomes

#### Treatment pattern

Treatment pattern is defined as:

- 1. Treatment discontinuation not related to treatment failure (treatment duration over, trying to become pregnant, other reasons)
- 2. Cohort status/switch of women during follow-up, considering the first treatment switch after baseline

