Pain severity score									
Mild (0-3)	xx ( xx.x%)	xx ( xx.x%)	xx ( xx.x%)	xx ( xx.x%)					

Supporting document SOP BMT 01.09 – Doc 5002.02 – Effective date 21.03.2017

Moderate (4-7) Severe (8-10)	xx ( xx.x%) xx ( xx.x%)								
Severe (8-10)	AA ( AA.A/0)	AA ( AA.A70)							
Switched to Danazol*	xx ( xx.x%)								
Age (years)									
Mean	xx.x								
SD	xx.xx								
Diagnosis classification									
Surgically confirmed diagnosis	xx ( xx.x%)								
Clinically confirmed diagnosis	xx ( xx.x%)								
Pain severity score									
Mild (0-3)	xx ( xx.x%)								
Moderate (4-7)	xx ( xx.x%)								
Severe (8-10)	xx ( xx.x%)								
Switched to CHC*	xx ( xx.x%)								
Switched to Other progestins*	xx ( xx.x%)								
 Switched to other EMT*	xx ( xx.x%)								
•••									

Note: \* Only the first stop or switch from baseline prescription is considered

Date of analysis:

Table B-9.4.2 Selected baseline characteristics for women who switched, Starter

Table B-9.4.3 Selected baseline characteristics for women who switched, Switcher

Table B-9.4.4 Selected baseline characteristics for women who switched, Restarter

Supporting document SOP BMT 01.09 - Doc 5002.02 - Effective date 21.03.2017

Section C Clinical Outcome

Section C-1 Primary outcomes

Section C-1.1 Incidence rate of clinically relevant anemia

Table C-1.1.1 Incidence rate of clinically relevant anemia, ITT population, Complete cohort

	DNG		OAED			NAED		Allocation unknown	Total
	-	GnRH-a	Danazol	All OAED	СНС	Other progestin	All NAED		
Number of women years	xx	XX	xx	XX	xx	xx	XX	xx	xx
Confirmed anemia	xx	xx	xx	xx	xx	xx	xx	XX	xx
IR* (95% CI)	xx.x (xx.x-x.x)	xx.x (xx.x-x.x)	xx.x (xx.x-x.x)	xx.x (xx.x-x.x)					
Thereof									
Treated with iron	xx	xx	xx	XX	XX	XX	XX	xx	xx
tablets	xx.x (xx.x-x.x)	xx.x (xx.x-x.x)	xx.x (xx.x–x.x)	xx.x (xx.x–x.x)	xx.x (xx.x–x.x)	xx.x (xx.x–x.x)	xx.x (xx.x-x.x)	xx.x (xx.x-x.x)	xx.x (xx.x-x.x)
Treated with iron	xx	xx	xx	xx	xx	XX	xx	xx	xx
infusions/injections	xx.x (xx.x-x.x)	xx.x (xx.x-x.x)	xx.x (xx.x–x.x)	xx.x (xx.x–x.x)	xx.x (xx.x–x.x)	xx.x (xx.x-x.x)	xx.x (xx.x–x.x)	xx.x (xx.x–x.x)	xx.x (xx.x-x.x)
Treated with blood	xx	xx	xx	xx	XX	XX	xx	XX	xx
transfusions	xx.x (xx.x–x.x)	xx.x (xx.x–x.x)	xx.x (xx.x–x.x)	xx.x (xx.x–x.x)	xx.x (xx.x-x.x)	xx.x (xx.x-x.x)	xx.x (xx.x-x.x)	xx.x (xx.x–x.x)	xx.x (xx.x–x.x)

Note: \* Incidence rate is shown per 10^4 women years.

Table C-1.1.2	Incidence rate of newly diagnosed or reoccurrence of anemia, AT population, Complete cohort

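### SAP mock tables B-8.12.1 to B-8.12.12 place women who stopped all treatment in a residual row labelled as a switch, so that row cannot separate stopping from switching

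*SAP*

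**What the plan says.** One secondary objective, in SAP section 2, reads in part: "To analyze the drug utilization pattern of DNG and other endometriosis treatments in a study population". SAP section 5.4.4 turns this into a treatment-pattern outcome with two items. Item 1 is discontinuation for reasons other than treatment failure. Item 2 is "Cohort status/switch of women during follow-up, considering the first treatment switch after baseline".

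Mock table B-8.12.1 serves item 2. Its parent row is "Switched or stopped EMT", with the note "Only the first switch or stop of the EMT prescribed at study entry is considered". Below it are rows for a switch to DNG, GnRH agonist, danazol, combined hormonal contraceptive and other progestin, and then "Switch to other EMT". The footnote to this last row lists its contents: "Women switched to other NAED, unspecific treatment (Multi-use, allocation unknown) or stopped EMT use (Ex-use"). Where time bands are spelled out, they are up to 6 months, 7 to 12 months and after 12 months. Tables B-8.12.2 to B-8.12.12 repeat the layout by user type, diagnosis classification and country.

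Mock table B-9.4.1, titled for women who switched, gives baseline characteristics by destination and ends with the row "Switched to other EMT". Its note says that the first stop or switch is considered.

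Elsewhere the SAP keeps stoppers apart. Section 5.1 states: "Women who stopped their treatment will be assigned to an" Ex-use cohort.

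**The concern.** A woman who takes no further endometriosis treatment is reported in a row that says she moved to another one. Stopping and switching are different utilization outcomes, and item 2 is defined by the switch.

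The group concerned may be large: SAP section 4 expects most women to stop or change treatment during the study. The mixing may also differ between cohorts. The protocol's introduction describes danazol and GnRH-agonist treatment as limited to 6-12 months, and SAP section 5.2 gives six months as the GnRH-agonist example. Completed courses that are followed by no treatment would fall into the first two time bands of the row and could be read as early switching by comparator users.

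**Working it through.** The tables are empty shells, so there is no figure of the plan to reproduce. The check is on structure.

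**1. Can stops be obtained by subtraction within B-8.12.1?** Let P be the parent row, N the sum of the five named destinations, and R the residual row. R is the sum of three parts: A (other NAED), U (unspecific or unknown) and S (stopped). The table gives P = N + R. Subtraction yields P − N = R = A + U + S, which is the pooled row again. There is no stop row and no Ex-use column, so S is not identified.

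**2. Is S available in another listed table?**

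- C-1.3 and C-2.1 use treatment starts as denominator, including later switches and restarts. They do not isolate the first change from the baseline prescription.
- Both classify by reason. SAP section 5.4.3 defines treatment failure by the reason given for stopping or switching, so C-1.3 does not say which of the two occurred. The C-2.1 row for finished treatment duration does not show whether another drug followed.
- Some follow-up mood tables (for example B-8.2.2) have an Ex-use column. It gives status at a visit, with cohorts formed by current use. It gives neither the first change nor the treatment that was left.

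No listed table gives the proportion of women whose first change was to stop all treatment.

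**3. B-9.4.1 to B-9.4.4.** Three facts point the same way. The note counts stops as well as switches. SAP section 8 describes this part of B-9 as covering women who stopped or switched. The only row that could hold stoppers is the residual one. No Ex-use footnote is attached to that row, so this is an inference.

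**4. Illustration of what the row can hide.** The stop shares are assumed, because the documents give none. Take 100 women in the parent row, s of whom stopped, and o other women in the residual row. The row shows s + o, and the stop share of the row is s / (s + o).

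| s (assumed) | o (assumed) | Row shows | Stops as share of row |
|---|---|---|---|
| 10 | 5 | 15 | 10/15 = 67% |
| 50 | 5 | 55 | 50/55 = 91% |
| 90 | 5 | 95 | 90/95 = 95% |
| 10 | 10 | 20 | 10/20 = 50% |
| 50 | 10 | 60 | 50/60 = 83% |
| 90 | 10 | 100 | 90/100 = 90% |

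In each line the rows labelled as switches add up to all 100 women, while 90, 50 or 10 of them did not stop. The range shows only that the row is uninterpretable without the split. It is not an estimate.

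**The case against.** The strongest reply is that nothing is concealed. The parent row names both events, one note says switch or stop, and the other lists Ex-use. The five named-destination rows and their time bands are correct as they stand. Treatment pattern also has two items, and planned end of treatment belongs to the first: C-2.1 has a row for it, with GnRH-agonist and danazol columns and confidence intervals. Stopping is therefore not absent from the utilization results. For B-9.4 the inclusion of stoppers is not stated in the row, and section 8 announces that stoppers are covered. All of this is descriptive.

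Each of these points stands and limits the scope. None of them makes the residual row readable: disclosure tells the reader that three groups were pooled but gives no means of separating them, and C-2.1 answers a different question with a different denominator.

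**Conclusion.** The point holds for one row in each B-8.12 table and, by inference, for the matching row in B-9.4. In that row the first-change part of the treatment-pattern outcome cannot distinguish stopping from switching, and no other listed table supplies the missing number. It is a flaw of labelling and separability in a descriptive secondary result. No primary outcome or hypothesis test is affected.

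A reader might infer more, and the documents do not support it:

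- *That the drug-utilization result as a whole reports stops as switches.* Only the residual row is mixed, and item 1 of the outcome is reported separately.
- *That switching is overstated by some multiple.* Any multiple depends on assumed stop shares, and the women in the row who did not stop include some with unknown allocation, who are not established switches either.
- *That GnRH agonists are affected most.* Danazol is described as time-limited too, and the documents do not say how many women stop, or move to another drug, after such a course. A difference between cohorts is plausible. Its direction and size are unknown.

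**What to change.** In B-8.12.1 to B-8.12.12, replace the residual row by three: switch to other NAED; unspecific treatment or allocation unknown; stopped EMT (Ex-use). Keep the time bands for each, and do not label the stop row as a switch. Make the same split in B-9.4.1 to B-9.4.4, with the existing age, diagnosis and pain sub-rows, and either retitle those tables to cover stopping or show stoppers under their own label.

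The cost is two additional rows, with their sub-rows, in 12 + 4 = 16 descriptive tables. No new data are needed: the follow-up questionnaire records dates of and reasons for stopping or switching, and the Ex-use category is already defined in SAP section 5.1.

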#### Section B-9 Summary tables of selected baseline characteristics

#### Section B-9.1 Selected baseline characteristics

Table B-9.1.1 Selected baseline characteristics, ITT population, Complete cohort

	DNG		OAED			NAED		Allocation unknown	Total
		GnRH-a	Danazol	All OAED	CC	Other progestin	All NAED		
Number (%) of women	xx ( 100%)	xx ( 100%)	xx ( 100%)	xx ( 100%)					
Age (years)									
Mean	xx.x	xx.x	xx.x	xx.x	xx.x	xx.x	XX.X	XX.X	xx.x
SD	xx.xx	xx.xx	xx.xx	XX.XX	xx.xx	xx.xx	xx.xx	xx.xx	XX.XX
BMI									
<20	xx ( xx.x%)	xx ( xx.x%)	xx ( xx.x%)	xx ( xx.x%)					
20 to <25	xx ( xx.x%)	xx ( xx.x%)	xx ( xx.x%)	xx ( xx.x%)					
25 to <30	xx ( xx.x%)	xx ( xx.x%)	xx ( xx.x%)	xx ( xx.x%)					
30 to <35	xx ( xx.x%)	xx ( xx.x%)	xx ( xx.x%)	xx ( xx.x%)					
≥35	xx ( xx.x%)	xx ( xx.x%)	xx ( xx.x%)	xx ( xx.x%)					
Missing	xx ( xx.x%)	xx ( xx.x%)	xx ( xx.x%)	xx ( xx.x%)					
Education									
Lower than university entrance level	xx ( xx.x%)	xx ( xx.x%)	xx ( xx.x%)	xx ( xx.x%)					
University entrance level	xx ( xx.x%)	xx ( xx.x%)	xx ( xx.x%)	xx ( xx.x%)					
Higher than university entrance level	xx ( xx.x%)	xx ( xx.x%)	xx ( xx.x%)	xx ( xx.x%)					
Missing	xx ( xx.x%)	xx ( xx.x%)	xx ( xx.x%)	xx ( xx.x%)					
Diagnosis classification									
Surgically confirmed diagnosis	xx ( xx.x%)	xx ( xx.x%)	xx ( xx.x%)	xx ( xx.x%)					

Supporting document SOP BMT 01.09 – Doc 5002.02 – Effective date 21.03.2017

Clinically confirmed diagnosis	xx ( xx.x%)								
Parity	xx ( xx.x%)								
Gravidity	xx ( xx.x%)								
Pain severity score									
Mild (0-3)	xx ( xx.x%)								
Moderate (4-7)	xx ( xx.x%)								
Severe (8-10)	xx ( xx.x%)								
Missing	xx ( xx.x%)								
Pain symptoms									
Pelvic pain	xx ( xx.x%)								
Pain during or after sexual intercourse	xx ( xx.x%)								
Painful periods	xx ( xx.x%)								
Personal history of Depression	xx ( xx.x%)								
Personal history of Anemia	xx ( xx.x%)								
Use of Antidepressants/SSRI	xx ( xx.x%)								

Table B-9.1.2	Selected baseline characteristics, AT population, Complete cohort
Table B-9.1.3	Selected baseline characteristics, AT population, Starter
Table B-9.1.4	Selected baseline characteristics, AT population, Switcher
Table B-9.1.5	Selected baseline characteristics, AT population, Restarter
Table B-9.1.6	Selected baseline characteristics, AT population, Diagnosis confirmed by surgery
Table B-9.1.7	Selected baseline characteristics, AT population, Diagnosis based on clinical symptoms
Table B-9.1.8	Selected baseline characteristics, AT population, Germany
Table B-9.1.9	Selected baseline characteristics, AT population, Poland
Table B-9.1.10	Selected baseline characteristics, AT population, Hungary
Table B-9.1.11	Selected baseline characteristics, AT population, Switzerland
Table B-9.1.12	Selected baseline characteristics, AT population, Russia
Table B-9.1.13	Selected baseline characteristics, AT population, Ukraine

Section B-9.2	Selected baseline characteristics by age categories
Table B-9.2.1	Selected baseline characteristics, Adolescence, ITT population
Table B-9.2.2	Selected baseline characteristics, Adolescence, AT population
Table B-9.2.3	Selected baseline characteristics, Women <20 years, ITT population
Table B-9.2.4	Selected baseline characteristics, Women <20 years, AT population
Table B-9.2.5	Selected baseline characteristics Women >=20 and < 30 years, ITT population
Table B-9.2.6	Selected baseline characteristics Women >=20 and < 30 years, AT population
Table B-9.2.7	Selected baseline characteristics, Women >=30 and < 40 years, ITT population
Table B-9.2.8	Selected baseline characteristics, Women >= 30 and < 40 years, AT population
Table B-9.2.9	Selected baseline characteristics, Women >=40 years, ITT population
Table B-9.2.10	Selected baseline characteristics, Women >=40 years, AT population
Table B-9.2.11	Selected baseline characteristics, age-standardized, ITT population
Table B-9.2.12	Selected baseline characteristics, age-standardized, AT population

Section B-9.3 Selected baseline characteristics for women with treatment failure

Table B-9.3.1 Selected baseline characteristics for women with treatment failure, AT population, Complete cohort

	DNG		OAED			NAED		Allocation unknown	Total
		GnRH-a	Danazol	All OAED	CC	Other progestin	All NAED		
Number (%) of women	xx ( 100%)	xx ( 100%)	xx ( 100%)	xx ( 100%)					
Medication ineffective as a reason for stopping or switching treatment* Age (years)	xx ( xx.x%)	xx ( xx.x%)	xx ( xx.x%)	xx ( xx.x%)					
Mean	XX.X	xx.x	xx.x	xx.x	XX.X	xx.x	XX.X	xx.x	xx.x
SD	xx.xx	xx.xx	xx.xx	xx.xx	xx.xx	xx.xx	xx.xx	xx.xx	xx.xx
Diagnosis classification									
Surgically confirmed diagnosis	xx ( xx.x%)	xx ( xx.x%)	xx ( xx.x%)	xx ( xx.x%)					
Clinically confirmed diagnosis	xx ( xx.x%)	xx ( xx.x%)	xx ( xx.x%)	xx ( xx.x%)					
Pain severity score									
Mild (0-3)	xx ( xx.x%)	xx ( xx.x%)	xx ( xx.x%)	xx ( xx.x%)					
Moderate (4-7)	xx ( xx.x%)	xx ( xx.x%)	xx ( xx.x%)	xx ( xx.x%)					
Severe (8-10)	xx ( xx.x%)	xx ( xx.x%)	xx ( xx.x%)	xx ( xx.x%)					
Side effects of medication as a reason for stopping or switching treatment	xx ( xx.x%)	xx ( xx.x%)	xx ( xx.x%)	xx ( xx.x%)					
Age (years)									
Mean	XX.X	xx.x	xx.x	xx.x	XX.X	XX.X	XX.X	XX.X	XX.X
SD	XX.XX	xx.xx	xx.xx	xx.xx	XX.XX	xx.xx	XX.XX	xx.xx	XX.XX
Diagnosis classification									
Surgically confirmed diagnosis	xx ( xx.x%)	xx ( xx.x%)	xx ( xx.x%)	xx ( xx.x%)					

Supporting document SOP BMT 01.09 – Doc 5002.02 – Effective date 21.03.2017

Clinically confirmed diagnosis	xx ( xx.x%)								
Pain severity score									
Mild (0-3)	xx ( xx.x%)								
Moderate (4-7)	xx ( xx.x%)								
Severe (8-10)	xx ( xx.x%)								

Note: \* Only the first stop or switch from baseline prescription is considered Date of analysis:

Table B-9.3.2 Selected baseline characteristics for women with treatment failure, AT population, Starter

Table B-9.3.3 Selected baseline characteristics for women with treatment failure, AT population, Switcher

Table B-9.3.4 Selected baseline characteristics for women with treatment failure, AT population, Restarter

Section B-9.4 Selected baseline characteristics for women who switched

Table B-9.4.1 Selected baseline characteristics for women who switched, AT population

	DNG		OAED			NAED		Allocation unknown	Total
		GnRH-a	Danazol	All OAED	CHC	Other progestin	All NAED		
Number (%) of women	xx ( 100%)	xx ( 100%)	xx ( 100%)	xx ( 100%)					
Switched to DNG*	xx ( xx.x%)	xx ( xx.x%)	xx ( xx.x%)	xx ( xx.x%)					
Age (years)									
Mean	XX.X	xx.x	xx.x	xx.x	XX.X	xx.x	xx.x	xx.x	xx.x
SD	XX.XX	xx.xx	xx.xx	xx.xx	xx.xx	xx.xx	xx.xx	xx.xx	xx.xx
Diagnosis classification									
Surgically confirmed diagnosis	xx ( xx.x%)	xx ( xx.x%)	xx ( xx.x%)	xx ( xx.x%)					
Clinically confirmed diagnosis	xx ( xx.x%)	xx ( xx.x%)	xx ( xx.x%)	xx ( xx.x%)					
Pain severity score									
Mild (0-3)	xx ( xx.x%)	xx ( xx.x%)	xx ( xx.x%)	xx ( xx.x%)					
Moderate (4-7)	xx ( xx.x%)	xx ( xx.x%)	xx ( xx.x%)	xx ( xx.x%)					
Severe (8-10)	xx ( xx.x%)	xx ( xx.x%)	xx ( xx.x%)	xx ( xx.x%)					
Switched to GnRH-a*	xx ( xx.x%)	xx ( xx.x%)	xx ( xx.x%)	xx ( xx.x%)					
Age (years)									
Mean	xx.x	xx.x	xx.x	xx.x	xx.x	xx.x	xx.x	xx.x	xx.x
SD	xx.xx	xx.xx	xx.xx	xx.xx	xx.xx	xx.xx	xx.xx	xx.xx	xx.xx
Diagnosis classification									
Surgically confirmed diagnosis	xx ( xx.x%)	xx ( xx.x%)	xx ( xx.x%)	xx ( xx.x%)					
Clinically confirmed diagnosis	xx ( xx.x%)	xx ( xx.x%)	xx ( xx.x%)	xx ( xx.x%)					
Pain severity score									
Mild (0-3)	xx ( xx.x%)	xx ( xx.x%)	xx ( xx.x%)	xx ( xx.x%)					

Supporting document SOP BMT 01.09 – Doc 5002.02 – Effective date 21.03.2017

Moderate (4-7) Severe (8-10)	xx ( xx.x%) xx ( xx.x%)								
Severe (8-10)	AA ( AA.A/0)	AA ( AA.A70)							
Switched to Danazol*	xx ( xx.x%)								
Age (years)									
Mean	xx.x								
SD	xx.xx								
Diagnosis classification									
Surgically confirmed diagnosis	xx ( xx.x%)								
Clinically confirmed diagnosis	xx ( xx.x%)								
Pain severity score									
Mild (0-3)	xx ( xx.x%)								
Moderate (4-7)	xx ( xx.x%)								
Severe (8-10)	xx ( xx.x%)								
Switched to CHC*	xx ( xx.x%)								
Switched to Other progestins*	xx ( xx.x%)								
 Switched to other EMT*	xx ( xx.x%)								
•••									

Note: \* Only the first stop or switch from baseline prescription is considered

Date of analysis:

Table B-9.4.2 Selected baseline characteristics for women who switched, Starter

Table B-9.4.3 Selected baseline characteristics for women who switched, Switcher

Table B-9.4.4 Selected baseline characteristics for women who switched, Restarter

Supporting document SOP BMT 01.09 - Doc 5002.02 - Effective date 21.03.2017

Section C Clinical Outcome

Section C-1 Primary outcomes

Section C-1.1 Incidence rate of clinically relevant anemia

Table C-1.1.1 Incidence rate of clinically relevant anemia, ITT population, Complete cohort

	DNG		OAED			NAED		Allocation unknown	Total
	-	GnRH-a	Danazol	All OAED	СНС	Other progestin	All NAED		
Number of women years	xx	XX	xx	XX	xx	xx	XX	xx	xx
Confirmed anemia	xx	xx	xx	xx	xx	xx	xx	XX	xx
IR* (95% CI)	xx.x (xx.x-x.x)	xx.x (xx.x-x.x)	xx.x (xx.x-x.x)	xx.x (xx.x-x.x)					
Thereof									
Treated with iron	xx	xx	xx	XX	XX	XX	XX	xx	xx
tablets	xx.x (xx.x-x.x)	xx.x (xx.x-x.x)	xx.x (xx.x–x.x)	xx.x (xx.x–x.x)	xx.x (xx.x–x.x)	xx.x (xx.x–x.x)	xx.x (xx.x-x.x)	xx.x (xx.x-x.x)	xx.x (xx.x-x.x)
Treated with iron	xx	xx	xx	xx	xx	XX	xx	xx	xx
infusions/injections	xx.x (xx.x-x.x)	xx.x (xx.x-x.x)	xx.x (xx.x–x.x)	xx.x (xx.x–x.x)	xx.x (xx.x–x.x)	xx.x (xx.x-x.x)	xx.x (xx.x–x.x)	xx.x (xx.x–x.x)	xx.x (xx.x-x.x)
Treated with blood	xx	xx	xx	xx	XX	XX	xx	XX	xx
transfusions	xx.x (xx.x–x.x)	xx.x (xx.x–x.x)	xx.x (xx.x–x.x)	xx.x (xx.x–x.x)	xx.x (xx.x-x.x)	xx.x (xx.x-x.x)	xx.x (xx.x-x.x)	xx.x (xx.x–x.x)	xx.x (xx.x–x.x)

Note: \* Incidence rate is shown per 10^4 women years.

Table C-1.1.2	Incidence rate of newly diagnosed or reoccurrence of anemia, AT population, Complete cohort
Table C-1.1.3	Incidence rate of newly diagnosed or reoccurrence of anemia, AT population, Starter
Table C-1.1.4	Incidence rate of newly diagnosed or reoccurrence of anemia, AT population, Switcher
Table C-1.1.5	Incidence rate of newly diagnosed or reoccurrence of anemia, AT population, Restarter
Table C-1.1.6	Incidence rate of newly diagnosed or reoccurrence of anemia, AT population, Diagnosis confirmed by surgery
Table C-1.1.7	Incidence rate of newly diagnosed or reoccurrence of anemia, AT population, Diagnosis based on clinical symptoms
Table C-1.1.8	Incidence rate of newly diagnosed or reoccurrence of anemia, AT population, Germany
Table C-1.1.9	Incidence rate of newly diagnosed or reoccurrence of anemia, AT population, Poland
Table C-1.1.10	Incidence rate of newly diagnosed or reoccurrence of anemia, AT population, Hungary
Table C-1.1.11	Incidence rate of newly diagnosed or reoccurrence of anemia, AT population, Switzerland
Table C-1.1.12	Incidence rate of newly diagnosed or reoccurrence of anemia, AT population, Russia
Table C-1.1.13	Incidence rate of newly diagnosed or reoccurrence of anemia, AT population, Ukraine

Supporting document SOP BMT 01.09 – Doc 5002.02 – Effective date 21.03.2017

